8.2.7. Neonatal Birth Record

Continuous variables, such as weight (g) and head circumference (cm) at neonatal birth record will be summarized. Also, APGAR at 1 and 5 minutes at birth will be summarized by reporting the number and percentage of subjects by treatment group. In addition, Neonatal Apgar scores at 1 and 5 minutes at birth will be presented categorically (≥ 7 or < 7)

All neonatal birth record data will be listed.

8.2.8. Placental Data

Placental data including chronic chorio, acute chorio, acute vasculitis, acute funisitis, remote infarction, recent infarction, post mature, intervillous thromb, villous infarctions, chronic villitis, acute villitis, inflammation, meconium will be summarized by treatment group. Also, the summary by GA category at randomization and time from start of IP until delivery will be presented.

All placental data will be listed.

8.3. Pharmacokinetic Analyses

The PK concentration data will be listing for plasma, cord blood and blood milk samples.

8.4. Biomarker Analyses

FFN results and cervical length will be presented in the baseline characteristics table. Also, the results will be listed. If applicable, inflammatory biomarker such as IL-6 will be summarized and listed.

Whenever applicable, the details of these additional analyses to explore the correlation of biomarker and the study effect will be described in a separate document.

9. DEVIATION OF PLANNED ANALYSES FROM PROTOCOL

No changes will be made to the planned analyses after the breaking of the study blind; however, due to the early termination of the study and the resultant low number of subjects enrolled in the study, not all originally planned data analyses, as outlined in the protocol, will be performed.

The following changes will be made to the planned analyses from the protocol:

- The following subgroup analyses for the primary and key secondary endpoints will not be performed.
 - Magnesium sulfate use
 - Putative tocolytic use following IP discontinuation
- Other exploratory covariate analyses will not be performed to examine the relationship between the treatment response and potential covariates including baseline fFN value, subclinical intrauterine infection, and other concomitant medications.
- Maternal and neonatal health outcomes will not be analysed but will be presented in data listings and analysis by subgroups will not be explored.

- Data will not be presented for neonatal ambulatory surgery as part of neonatal health care resource use results.
- No formal interim analyses will be performed.
- The PK data will be not analysed but will be listed for plasma, cord blood and blood milk samples.
- No analysis for retosiban clearance and volume of distribution and the effect of covariates on these parameters will be performed.
- Newborn hospital readmission and length of stay will not be analysed but will be listed.
- Incidence of treatment-limiting toxicities including both clinical and laboratory etiology causing subject to discontinue study treatment will not be analysed.
- No analysis for Edinburgh Postnatal Depression Scale and EQ-5D-5L will be performed.
- No analysis using per-protocol (PP) population will be performed.

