6.3. Safety

The timing for all safety assessments is outlined in the Time and Events Schedule [Table 5](#).

Maternal:

- Incidence of reported AEs and SAEs
- Significant changes in vital signs and clinical laboratory tests
- Incidence of treatment-limiting toxicities including both clinical and laboratory etiology causing subject to discontinue study treatment

- Maternal AEs of special interest
 - Maternal death
 - Chorioamnionitis and its complications
 - Clinical chorioamnionitis, PPROM, endomyometritis, wound infection, pelvic abscess, bacteremia, septic shock, disseminated intravascular coagulation, and adult RDS
 - Placental abruption
 - Postpartum hemorrhage - postpartum hemorrhage and/or retained placenta (as assessed by AEs, time to expulsion of the placenta, assessment of uterotonic agents used, and change in hemoglobin from baseline value to 24 to 48 hours post-delivery adjusting for mode of delivery)
 - Pulmonary edema
- Incidence of women scoring 12 or higher on the EPDS

Fetal:

- Incidence of reported AEs, including SAEs
- Fetal acidosis
- Fetal AEs of special interest
 - Intrauterine fetal demise
 - Category II or III fetal heart rate tracing (defined according to ACOG Practice Bulletin 106 [[ACOG](#), 2009])
 - Fetal inflammatory response syndrome characterized by cord blood interleukin-6 >11 pg/mL, funisitis, or chorionic vasculitis

Neonatal:

Note: Information collected from the time of birth through 28 days post EDD.

- Neonatal Apgar scores (at 1 and 5 minutes after birth), growth parameters (weight, length, and head circumference) at birth and at discharge, and documentation of any complications
- Incidence of reported AEs and SAEs
- Neonatal AEs of special interest are of interest because of their relationship to maternal chorioamnionitis and will include the following:
 - Neonatal death
 - Asphyxia
 - Infections (early onset neonatal sepsis, septic shock, pneumonia, meningitis)
 - RDS
 - Hypotension

- IVH/periventricular leukomalacia with cysts or porencephaly
- Bronchopulmonary dysplasia
- Neonatal acidosis
- Hyperbilirubinemia
- Necrotizing enterocolitis (any modified Bell's staging criteria)
- Hypoxic ischemic encephalopathy

Maternal and neonatal disease-related events (DREs) to be reported are described in Section 6.3.7.

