8.3.5.2. Safety Analyses

No formal hypothesis statistical test will be performed for the safety data. All safety analyses will be done using the safety population, unless otherwise specified. The objective of the safety analysis is to describe the maternal, fetal, and neonatal safety profile during/after IV retosiban treatment as compared with atosiban treatment. As such, maternal, fetal, and neonatal safety data will be summarized by treatment group.

All summary statistics of continuous variables will include: n, mean, median, standard deviation, minimum, and maximum. For binary outcomes, all summary tables will include the number and percentage of subjects with the response/event. All summary tables will include N for each group (i.e., the total number of subjects randomly assigned to each group within the appropriate population).

To further describe the maternal, fetal, and neonatal safety profile of retosiban, the following subgroups may be explored:

- GA of pregnancy at randomization
- Established progesterone use
- GA at delivery
- Maternal age
- Region/site

For each subgroup, maternal, fetal, and neonate safety data will be summarized by treatment and subgroup, as described above.

8.3.5.2.1. *Extent of Exposure (Maternal)*

The total volume administered during the infusion and the total volume administered overall will be summarized. If applicable, the number of infusion interruptions and the time taken for each infusion will be summarized. The frequency and percentage of women who discontinued study treatment and reason for discontinuation and who increased study treatment from 6 to 12 mg will be summarized.

8.3.5.2.2. *Adverse Events*

Adverse events will be coded using the MedDRA dictionary and grouped by body system. Adverse events will be summarized by treatment group. Within each group, AEs will be summarized by frequency and proportion of total subjects, by event type, and by category of body system. Separate summaries will be given for all AEs, drug-related AEs, SAEs, and AEs leading to discontinuation. Where appropriate, each phase of the study (pretreatment, treatment, and follow-up) will be tabulated separately.

The proportion of subjects reporting at least 1 AE, 1 IP-related AE, 1 SAE, and 1 AE leading to discontinuation will also be calculated for each group.

Adverse events of special interest (see Section 6.3.2.3) and DREs (see Section 6.3.7) will be similarly summarized.

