8.2.3.5. Adverse Events Leading to Treatment Discontinuation

A listing of all AEs leading to permanent discontinuation of study drug and/or withdrawal from the study will be produced if applicable.

The AEs leading to permanent discontinuation will be summarized only for maternal events if applicable.

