11.11. Appendix 11: List of Data Displays

A separate document for shells contains all table, listing and figures' (TLFs) for the planned final analysis. However, due to early termination of the study, only TLFs listed in this appendix will be generated.

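### AEs that stopped the infusion, a stated maternal safety endpoint, and drug-related AEs have no by-arm display in SAP Appendix 11, and SAP 2.2, 8.2.3.5, 9 and Appendix 11 do not agree

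*SAP*

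**What the plan says.** **Protocol.** Section 6.3 lists among the maternal safety endpoints: "Incidence of treatment-limiting toxicities including both clinical and laboratory etiology causing subject to discontinue study treatment". Under Adverse Events, Section 8.3.5.2 commits to by-group reporting: "Separate summaries will be given for all AEs, drug-related AEs, SAEs, and AEs leading to discontinuation". It adds that the proportion of subjects with at least one such event is reported per arm: "1 AE leading to discontinuation will also be calculated for each group". The same sentence promises the proportion with at least one AE related to the investigational product (IP).

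**SAP, endpoint and text.** The SAP was written after the study had been terminated with 97 women randomised. Section 2.2 still lists the endpoint for the mother. Section 8.2.3.5 plans a listing ("A listing of all AEs leading to permanent discontinuation of study drug and/or withdrawal from the study will be produced if applicable") and a summary ("The AEs leading to permanent discontinuation will be summarized only for maternal events if applicable"). Both sentences are conditional.

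**SAP, deviations.** Section 9 says: "Incidence of treatment-limiting toxicities including both clinical and laboratory etiology causing subject to discontinue study treatment will not be analysed". A bullet close by keeps a listing for a different endpoint ("Newborn hospital readmission and length of stay will not be analysed but will be listed"); the toxicity bullet has no such clause.

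**SAP, outputs.** Appendix 11 (Section 11.11) states: "due to early termination of the study, only TLFs listed in this appendix will be generated".

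**The concern.** The sections give different answers to a simple question: will the report say how many women in each arm stopped the infusion because of an adverse event? Section 8.2.3.5 says yes, if there are any. Section 9 says the endpoint is not analysed. Appendix 11, which governs what is programmed, has no place for the result. A programmer following Appendix 11 would leave a stated safety endpoint, and two per-group proportions promised in the protocol, without a dedicated result.

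Section 9 gives the low number of subjects as the reason for dropping analyses. That is a sound reason for dropping models. It is a weak reason here, because the endpoint is purely descriptive: Protocol 8.3.5.2 and SAP 5.2 both exclude formal testing of safety data.

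**Working it through.** No sample size, power or alpha figure is involved, so there is no plan figure to reproduce. The check is a reconciliation of sections, followed by a short calculation of what a count could show.

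**1. AEs leading to discontinuation**

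| Place | Status |
|---|---|
| Protocol 6.3 | maternal safety endpoint |
| Protocol 8.3.5.2 | by-group summary and per-group proportion |
| SAP 2.2 | endpoint retained |
| SAP 8.2.1, Table 5 | no row |
| SAP 8.2.3.5 | 1 listing and 1 maternal summary, if applicable |
| SAP 9 | not analysed; no listing mentioned |
| SAP 11.11.5, maternal AE tables (3.11, 3.31, 3.41, 3.51, 3.71, 3.72, 3.81) | 0 tables |
| SAP 11.11.6 and 11.11.7, listings | 0 listings |

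The condition in 8.2.3.5 does not reconcile these. If such events did occur, Appendix 11 would still have no display for them.

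**2. Drug-related AEs**

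Protocol 8.3.5.2 promises a summary and a per-group proportion. SAP 11.3.3 derives the drug-related flag. No Appendix 11 title refers to it, and the list of changes in SAP 9 does not mention the removal.

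**3. What the retained displays give**

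- Table 1.01 covers IP discontinuation by treatment group, with reasons (content in SAP 6.2). Listing 3 gives the reasons by subject. Both use the All Randomized population, which SAP 4 presents by planned arm and which includes women who were never dosed. SAP 11.4.3 calls for actual treatment in safety reporting.
- A reason is not necessarily an event. Protocol 4.4.2 includes labour progression, delivery and obstetric indications among the grounds for stopping.
- Table 3.11 and Listing 41 give all maternal AEs. Neither title says that the events which stopped the infusion are identified.

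The loss is therefore specific: n (%) by actual treatment, in the Maternal Safety Population, of women with an AE that led to stopping IP, and of women with a drug-related AE.

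**4. Can a count be informative at this size?**

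Input: 97 randomised 1:1 (SAP 2.3), so 97 / 2 = 48.5, or 48 to 49 per arm. The number dosed is not stated, so 48 is an assumption and 40 is used as a lower case.

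- Exact two-sided 95% upper limit with zero events: 1 − 0.025^(1/n).
 - n = 48: 1 − 0.025^(1/48) = 7.4%.
 - n = 40: 1 − 0.025^(1/40) = 8.8%.
- Chance of at least one event among 48 women: 1 − (1 − p)^48. For assumed true rates p of 1%, 2%, 5% and 10% this is 38%, 62%, 91% and 99%.

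Even an empty table would put a ceiling on the rate, and at a true rate of 5% an event would very probably be seen.

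**The case against.** The case for leaving the plan alone has several parts.

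- **Not analysed may not mean not summarised.** Section 9 also says that health outcomes will not be analysed, yet Appendix 11 keeps summary Tables 3.301 and 3.463. This stands, and it softens the conflict between Sections 9 and 8.2.3.5. It does not touch the mismatch between 8.2.3.5 and Appendix 11.
- **The two terms differ.** Section 8.2.3.5 speaks of AEs leading to discontinuation and does not name treatment-limiting toxicity. That is correct, but the endpoint is itself defined by causing discontinuation, so this is the only section that could deliver it.
- **Much is retained.** A reader might infer that tolerability by arm goes unreported. The documents do not support that: discontinuation reasons by randomised arm and all maternal AEs by arm remain, and Listing 1 lets a reader match each subject to her actual treatment.
- **The table shells are in a separate document.** Listing 3 or Listing 41 may show action taken or relatedness. This cannot be excluded from titles alone. A listing column would still not be a by-arm count.
- **The omission may be deliberate.** Appendix 11 has numbering gaps and separate listings for only some AEs of special interest, which would fit pruning to displays that have data. That is possible but not stated, and a zero count is itself a safety result.
- **Concealment.** A reader might infer that the endpoint was dropped silently. It was not: Section 9 declares it. Only the drug-related summary disappears without a declaration.

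**Conclusion.** The point holds in a limited form. SAP 2.2, 8.2.3.5, 9 and Appendix 11 need to be reconciled. If Appendix 11 is followed as written, two by-arm safety counts promised in the protocol are not produced: AEs that led to stopping IP, and drug-related AEs. The first omission is declared but conflicts with 8.2.3.5; the second is not declared. The primary analysis is unaffected. The change should be made because it is cheap and concerns safety.

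The size should not be overstated. A reader might infer that a count at this sample size would tell a well-tolerated infusion from a poorly tolerated one. It would not do so reliably. As an invented illustration, 0/48 has an exact 95% interval of 0 to 7.4% and 5/48 has about 3.5% to 22.7%. These overlap, and Fisher's exact test for 0/48 against 5/48 gives p = 0.056. The supportable claim is that a count bounds the rate: at 7.4% with zero events if about 48 women per arm were dosed, and at 8.8% if 40 were. Both figures rest on an assumed number dosed.

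The finding on displays rests on Appendix 11 titles, because the shells are not available.

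**What to change.** 1. In SAP 9, replace the bullet with a statement that the endpoint will be summarised descriptively only, as n (%).
2. Add to Appendix 11 one table and one listing of maternal AEs leading to permanent IP discontinuation, in the Maternal Safety Population by actual treatment, with zero counts shown if there are none. Remove the conditional wording from 8.2.3.5 so that the sections match.
3. Add to Appendix 11 the drug-related AE table, using the flag in SAP 11.3.3. That flag counts a missing relationship as related, so the table should carry a footnote saying so.

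The cost is two short tables, one listing and a few lines of SAP wording. All of it uses data the protocol already has sites collect.

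A lesser option is to delete the plan in 8.2.3.5, say that only disposition reasons will be reported, and declare the drug-related omission in Section 9. That would remove the contradiction but still leave the protocol's two per-group proportions unreported.

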11. APPENDICES

Section	Appendix
RAP Section 4 : Analysis Populations	
Section 11.1	Appendix 1: Protocol Deviation Definitions
RAP Section 5 : General Considerations for Data Analyses & Data Handling Conventions	
Section 11.2	Appendix 2: Time and Events
Section 11.3	Appendix 3: Treatment States and Phases
Section 11.4	Appendix 4: Data Display Standards & Handling Conventions 
 • Study Treatment & Sub-group Display Descriptors • Baseline Definitions & Derivations • Reporting Process & Standards
Section 11.5	Appendix 5: Derived and Transformed Data 
 • General, Study Population & Safety • Efficacy
Section 11.6	Appendix 6: Premature Withdrawals & Handling of Missing Data 
 • Premature Withdrawals • Handling of Missing Data
Section 11.7	Appendix 7: Primary and Sensitivity Analyses for Primary and Key Secondary Endpoints with Missing Data 
 • Time to Delivery • Neonatal Composite Outcome • Proportional of Preterm Birth <37 weeks or \geq 37 weeks • Length of Hospital Stay • Error! Reference source not found.
Section 11.8	Appendix 8: Values of Potential Clinical Importance 
 • Laboratory Values for Pregnant Women • Vital Signs for Pregnant Women • Fetal Heart Rate
Section 11.9	Appendix 9: Model Checking and Diagnostics for Statistical Analyses
Other RAP Appendices	
Section 11.10	Appendix 10: Abbreviations & Trade Marks
Section 11.11	Appendix 11: List of Data Displays

11.1. Appendix 1: Protocol Deviation Definitions

Subject compliance to the protocol will be evaluated prior to database freeze and unblinding the study and subjects with significant protocol deviations will be identified. Specific criteria for what constitutes a major protocol violation will be determined by the study team and the following criteria will be considered:

Maternal Major Protocol Violation

- Not meeting inclusion criteria 3 (Gestational age between 24^{0/7} and 33^{6/7} weeks as determined by (1) known fertilization date, either in vitro fertilization or intrauterine insemination or (2) a best estimated due date confirmed or established by the earliest ultrasound performed before 24^{0/7} weeks gestation.)

11.2. Appendix 2: Time and Events

Procedures	Screening Phase	Inpatient Randomized Treatment Phase		Retreatment ¹	Post-Infusion Assessment Phase ²		Delivery Phase	Maternal Post-Delivery Assessment Phase (via Telephone)	Neonatal Medical Review Phase	Withdrawal From Study
	Day 0	Day 1	Day 2	(Optional – 1 time only)	Face-to-face post-infusion visit	Weekly post-infusion telephone call	Information collected via medical records review	6 weeks after delivery ³	Delivery to 28 days post EDD	
Clinical and Other Assessments										
Written informed consent and medical releases for treatment ⁴	X									
Discuss and request consent for participation in the infant follow-up study ⁵										X
X ⁵ ←								→ X		
Inclusion/exclusion criteria confirmation	X			X						
Subject demography	X									
Medical history (including obstetrics history) ⁶	X				X		X	X		
Physical examination (including height and weight)	X									
Cervical examination ⁷	X	X	X	X	X					
Estimated fetal weight and head circumference via ultrasound ⁸	X			X						

CONFIDENTIAL

GSK200721

Procedures	Screening Phase	Inpatient Randomized Treatment Phase		Retreatment ¹	Post-Infusion Assessment Phase ²		Delivery Phase	Maternal Post-Delivery Assessment Phase (via Telephone)	Neonatal Medical Review Phase	Withdrawal From Study
	Day 0	Day 1	Day 2	(Optional – 1 time only)	Face-to-face post-infusion visit	Weekly post-infusion telephone call	Information collected via medical records review	6 weeks after delivery ³	Delivery to 28 days post EDD	
Determine AFI via ultrasound ⁹	X			X						
Uterine contractions ¹⁰	X									
Schedule face-to-face post-infusion assessment visit			X							
Investigational Products¹¹										
Investigational product (retosiban or atosiban)		X	X	X						
Efficacy Assessments										
Date and time of delivery								X ¹²		
Mode of delivery								X ¹²		
Indication for delivery								X ¹²		
Neonatal composite outcomes									X	
Neonatal hospital stay									X	

Procedures	Screening Phase	Inpatient Randomized Treatment Phase		Retreatment ¹	Post-Infusion Assessment Phase ²		Delivery Phase	Maternal Post-Delivery Assessment Phase (via Telephone)	Neonatal Medical Review Phase	Withdrawal From Study
	Day 0	Day 1	Day 2	(Optional – 1 time only)	Face-to-face post-infusion visit	Weekly post-infusion telephone call	Information collected via medical records review	6 weeks after delivery ³	Delivery to 28 days post EDD	
Maternal Safety Assessments										
Concomitant medications				X ←				→ X		X
ECG 12-lead ¹³	X									
Vital sign measurements (BP, pulse rate, respiratory rate, and temperature) ¹⁴	X	X	X	X	X					
AEs, SAEs, and DREs: maternal			X ←					→ X		X
Breastfeeding status									X	
Edinburgh Postnatal Depression Scale ¹⁵ (maternal)									X	
Local laboratory assessments (LFTs only) ¹⁶	X			X						
Central laboratory assessments (including hematology, chemistry, and LFTs) ¹⁷	X		X	X	X ¹⁷					
Physical examination (brief)					X					
Status of postpartum bleeding									X	

Procedures	Screening Phase	Inpatient Randomized Treatment Phase		Retreatment ¹	Post-Infusion Assessment Phase ²		Delivery Phase	Maternal Post-Delivery Assessment Phase (via Telephone)	Neonatal Medical Review Phase	Withdrawal From Study
	Day 0	Day 1	Day 2	(Optional – 1 time only)	Face-to-face post-infusion visit	Weekly post-infusion telephone call	Information collected via medical records review	6 weeks after delivery ³	Delivery to 28 days post EDD	
Fetal Safety Assessments										
Electronic fetal monitoring	X ¹⁸	X ¹⁹	X ¹⁹	X ¹⁹	X ²⁰		X ²¹			
AEs/SAEs: fetal			X ← → X							
Neonatal Safety Assessments										
AEs, SAEs, and DREs: neonatal							X ← → X			
Neonatal Apgar Scores (1 and 5 minutes)							X ¹²			
Neonatal growth parameters							X ¹²			
Neonatal blood gases							X ¹²			
Health Outcome Assessments										
Maternal and neonatal health care resource use ²²							X		X	
EQ-5D-5L (maternal)		X						X ³		
Pharmacokinetic Assessments										
Maternal PK blood sample ²³		X ²³	X ²³							
Cord blood sample ²⁴							X			
Breast milk/colostrum sample ²⁵							X			
Histopathology										
Placental tissue sample ²⁶							X			

Procedures	Screening Phase	Inpatient Randomized Treatment Phase		Retreatment ¹	Post-Infusion Assessment Phase ²		Delivery Phase	Maternal Post-Delivery Assessment Phase (via Telephone)	Neonatal Medical Review Phase	Withdrawal From Study
	Day 0	Day 1	Day 2	(Optional – 1 time only)	Face-to-face post-infusion visit	Weekly post-infusion telephone call	Information collected via medical records review	6 weeks after delivery ³	Delivery to 28 days post EDD	
Biomarker Assessments										
Genetic blood sample for maternal DNA ²⁷	X									
Blood sample for maternal inflammation biomarker	X									
Biomarker and genetic cord blood sample ²⁸							X			
Other Assessments										
Fetal fibronectin (optional) ²⁹	X			X						
Cervical length via transvaginal ultrasound (optional) ³⁰	X			X						

AE = adverse event; AFI = amniotic fluid index; ALT = alanine aminotransferase; BP = blood pressure; DRE = disease-related event; ECG = electrocardiogram; eCRF = electronic case report form; EDD = estimated date of delivery; EPDS = Edinburgh Postnatal Depression Scale; EQ-5D-5L = EuroQol 5-dimensional 5-level questionnaire; IP = investigational product; LFT = liver function test; PK = pharmacokinetic; SAE = serious adverse event; ULN = upper limit of normal.

1. For undelivered subjects who are subsequently diagnosed with recurrent preterm labor 24 hours or more following completion of the Inpatient Randomized Treatment Phase, retreatment with blinded IP is permitted at the discretion of the investigator (see Protocol Section 3.1.3.1).
2. Subjects who remain undelivered after 48 hours will return for a face-to-face post-infusion assessment visit for obstetric assessments 1 week (acceptable range: 3 to 14 days) following the Inpatient Randomized Treatment Phase. (Note: study documents may reference this visit as the 1-week face-to-face post-infusion assessment visit). The subject will then be contacted every week via telephone to determine if she has delivered or experienced any subsequent episodes of preterm labor. Note: If the subject is scheduled to visit the clinic for reasons not required by this protocol and/or she happens to be present at the time the telephone assessment is due, this assessment may be completed face-to-face. If the subject delivers the baby prior to the face-to-face post-infusion assessment visit, central laboratory assessments for hematology, chemistry, and LFTs and the assessments for the Delivery Phase (see Protocol Section 3.1.4) will be performed.

3. During the Maternal Post-Delivery Assessment Phase, subjects will be contacted by telephone within 6 weeks of delivery for a post-delivery assessment, including an assessment of AEs (± 2 weeks), status of breastfeeding (± 2 weeks), and completion of the EPDS (-2 weeks/+6 weeks) and the EQ-5D-5L (-2 weeks/+6 weeks) (see Protocol Section 3.1.5 for list of assessments and visit windows).
4. Prestudy screening information that is collected by the study site may need to come from records that are obtained before the subject has signed the informed consent. The subject will be required to provide written informed consent before any study-specific procedures are performed, and the consent will request permission for use of any information collected prior to its having been signed.
5. The subject or other legal guardian for the infant will be asked to consent to participate in a separate long-term study to follow infants for safety and neurodevelopment outcomes. The subject or other legal guardian for the infant (both delivered and undelivered) will be asked to give consent for the infant follow-up study at any time during the study that is appropriate and convenient. Withdrawal from the study after beginning randomized treatment or discontinuing IP does not preclude involvement in the infant follow-up study.
6. Medical history will be collected at Screening. If a condition with a start date predating Day 0 (Screening) is subsequently discovered, the condition should be recorded in the Medical History eCRF. For obstetrics history, the investigator will make every effort to obtain this information either via computer records, directly from the subject's primary care obstetrician, or via telephone. However, in cases in which these records are not readily available (e.g., off hours, holiday), it is within the investigator's discretion to use gestational age based on the verbal history from the subject with the intent of getting confirmation from the medical records as soon as possible.
7. A cervical examination (including dilation, effacement, and station) will occur at Screening, and an additional cervical examination may be performed before dosing based on investigator discretion. Additional cervical examinations (Day 1, Day 2, and/or at the face-to-face post-infusion assessment visit) are not required but may be performed based on investigator discretion. If inclusion criteria are based on cervical change (see Protocol Section 4.2), 2 examinations must be documented (either 2 digital cervical examinations or 2 cervical length examinations).
8. An ultrasound for estimation of fetal weight and head circumference is needed at Screening or before retreatment unless the date of the most recent ultrasound that includes fetal weight and head circumference is within 3 weeks (21 days) of the date of randomization or the date of retreatment.
9. The abdominal ultrasound for determination of the AFI will be performed at Screening and before retreatment. The AFI should be measured using the 4-quadrant method.
10. Uterine tocography or manual palpation (if necessary) will be performed at Screening. Manual palpations will be permitted if there are technical challenges with measuring contraction frequency.
11. Antenatal corticosteroid treatment should be administered in accordance with national, society, or institutional guidelines. Magnesium sulfate for fetal neuroprotection can be given at the discretion of the investigator.
12. Information regarding delivery will be obtained through a review of the hospital and medical records. Growth parameters include neonatal weight, length, and head circumference.
13. A 12-lead ECG will be performed prior to dosing. If the results are interpreted by the investigator to have clinically significant abnormalities, the subject cannot be dosed.
14. Vital signs (blood pressure, pulse rate, respiratory rate, and temperature) will be assessed at Screening, as part of maternal safety monitoring during the Inpatient Randomized Treatment Phase and, if criteria are met, also during retreatment, and at the post-infusion assessment visit. During the Inpatient Randomized Treatment Phase and during retreatment, vital signs will be assessed and recorded within the following windows relative to the start of the infusion: 15 to 30 minutes, 4 to 8 hours, and 20 to 24 hours, at the end of the infusion, at the time of any dose changes, and as warranted by a medical condition. It is suggested (but not required) that oxygen saturation also be assessed at Screening and recorded in source documents.
15. Maternal subjects will complete the EPDS, a self-reported questionnaire, at the maternal follow-up assessment 6 weeks (-2 weeks/+6 weeks) after delivery.
16. The LFTs should be ordered from the local laboratory before dosing with the IP. If the local laboratory results are available before the start of dosing, confirm that ALT is not $\geq 2 \times$ ULN OR total bilirubin is not $>1.5 \times$ ULN ($>35\%$ direct bilirubin). An isolated bilirubin $>1.5 \times$ ULN is acceptable if bilirubin is fractionated and direct bilirubin is $<35\%$. Screening LFT laboratory results do not need to be available for the subject to be randomly assigned to treatment or for the start of dosing with IP; however, see Protocol Section 6.3.1 if ALT or bilirubin is abnormal.

17. Hematology, chemistry, and LFTs will be determined through a central laboratory at the screening, Day 2, and the face-to-face post-infusion assessment visits. The LFT values from the central laboratory should be reviewed for abnormalities (see Protocol Section 6.3.1). For subjects who deliver within 24 hours after completion or discontinuation of IP and for subjects who deliver at the investigative center after discharge but before the face-to-face post-infusion assessment visit, central laboratory assessments for hematology, chemistry, and LFTs should be performed. For subjects that do not deliver at the investigative center, central laboratory assessments for hematology, chemistry, and LFTs should be performed at the investigative center within 1 week (acceptable range: 3 to 14 days) after completion of the study drug infusion.
18. Prior to dosing, if the fetal heart rate pattern is nonreassuring, the subject cannot be dosed.
19. Electronic fetal monitoring is required for a minimum of 6 hours from the start of the infusion or from the start of a dose increase. As long as the fetal heart rate pattern is consistently reassuring throughout the required 6-hour duration of monitoring and the contraction frequency is ≤ 2 in a 30-minute window within the last hour of monitoring, continuous monitoring may be discontinued and nonstress tests initiated at a minimum of every 8 hours and as needed. Electronic fetal monitoring, including the fetal heart rate and fetal heart rate category, will be recorded in the eCRF with maternal vital signs. Any fetal heart rate assessment of Category II or III will be reported as an AE of special interest on a specified eCRF (details in Protocol Section 6.3.12.3**Error! Reference source not found.**).
20. If the subject has not delivered at the end of the Inpatient Randomized Treatment Phase, fetal heart rate (fetal Doppler heart rate or cardiotocography are both acceptable) will be recorded at the face-to-face post-infusion assessment visit. Any fetal heart rate assessment of Category II or III will be reported as an AE of special interest on a specified eCRF (details in Protocol Section 6.3.12.3).
21. During the Delivery Phase, fetal heart rate just prior to delivery will be collected, if available, from review of delivery records. Any fetal heart rate assessment of Category II or III will be reported as an AE of special interest on a specified eCRF (details in Protocol Section 6.3.12.3).
22. Maternal and neonatal health care resource use may include, but is not limited to, neonatal complications requiring intensive or specialized care, neonatal hospital readmission, and neonatal ambulatory surgery.
23. PK samples will be taken at the following sampling windows (relative to the start of the infusion): 2 to 4 hours, 10 to 14 hours, 22 to 26 hours, and 48 to 54 hours. In addition, a PK sample should be taken at the onset of any maternal or fetal SAE that occurs within 12 hours after completion or discontinuation of IP. A maternal blood sample should be collected at the same time as the cord blood sample (see Protocol Section 6.5.1) if the sample time does not already coincide with one of the PK sampling windows.
24. In subjects who deliver at an investigative center within 12 hours following completion or discontinuation of the IP, the cord blood sample will also be divided for PK analysis as well as genetic (if additional consent is provided; Protocol Appendix 1) and biomarker analyses.
25. A breast milk/colostrum sample is only to be collected in women who deliver and produce breast milk within 12 hours after completion or discontinuation of the IP.
26. A placental tissue sample will be collected at delivery in subjects who deliver at an investigative center.
27. A maternal blood sample for genetic research will only be collected from subjects who provide separate informed consent (see Protocol Appendix 1).
28. A cord blood sample will be collected in subjects who deliver at an investigative center, if additional consent is provided.
29. Testing for fetal fibronectin will be performed only at those institutions collecting the information as routine practice. Fetal fibronectin will not be used to determine study eligibility.
30. Cervical length measured by transvaginal ultrasound will be captured only at those institutions collecting the information as routine practice. Cervical length will not be used to determine study eligibility.

